- 3) To assess the effect of treprostinil inhalation on oxygenation in patients with acute hypoxic respiratory failure with, or at risk for, development of ARDS
- 4) To assess the effect of treprostinil inhalation on various biomarkers thought to be related to the pathogenesis and/or clinical course of ARDS.

We propose a proof of concept, double blinded, placebo controlled study of inhaled treprostinil for patients with "at-risk" or early ARDS. Early, or pre-ARDS will be defined as acute hypoxemia and unilateral pulmonary infiltrates in patients presenting with conditions that are conducive to ARDS (e.g. pneumonia, sepsis, aspiration, trauma) but do not yet meet criteria for ARDS: require mechanical ventilation, bilateral infiltrates on CXR, and PaO_2/FiO_2 ratio < 300. The primary outcome will be PaO_2/FiO_2 ratio. We will also measure other physiologic and clinical outcomes and levels of inflammatory and pro-fibrotic biomarkers. This exploratory initial study will enroll 30 patients to assess feasibility and safety in this population.

Hypothesis:

- 1. Treprostinil inhalation is safe at planned dose titration in patients with acute hypoxemic respiratory failure
- 2. Treprostinil will improve oxygenation and other secondary outcomes related to mechanical ventilation initiation and duration, as well as exhibit effects on ARDS-related pro-inflammatory and pro-fibrotic biomarkers.

Study Design:

- 1) Single Center, proof of concept, 2:1 active drug to placebo controlled, double-blinded
- 2) Target of 30 patients enrolled
- 3) Patients will be randomized to receive either treprostinil or saline inhalation placebo
- 4) Patients will be followed to hospital discharge or day 28, whichever comes first. Those discharged prior to day 28 will be assumed free of mechanical ventilation and alive unless readmitted in that period. This will be confirmed by phone.

Sample Size/Interim Monitoring:

1) This is primarily a feasibility, safety and proof of concept trial.

Version: 02-09-2018

- 2) The primary endpoint is Change in PaO₂/FiO₂ ratio from Study Day 0 to 2, 7
- 3) Trial progress will be monitored by an independent Data and Safety Monitoring Board to determine if the study should stop for safety reasons. The first interim review will occur6 months following enrollment of the first patient or after the first 15 patients (which-ever occurs first) have been enrolled.

Inclusion Criteria:

- 1) Adults age 18-80 years.

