- 2) Acute onset need for 4 LPM or more of supplemental oxygen to maintain $PaO_2 > 60$ mmHg or arterial O_2 saturation > 90% by pulse oximetry.
- Acute unilateral pulmonary infiltrate/s on chest radiograph with no clinical evidence of left-sided heart failure. Bilateral infiltrates are acceptable as long as all other inclusion/exclusion criteria are met.

"Acute onset" is defined as follows: the duration of the hypoxemia criterion (#2) must be less than 96 hours and the chest radiograph criterion (#3) must be ≤ 28 days at the time of randomization. We acknowledge there is some difficulty determining absolute acuity with a 28 day window for the chest radiograph criterion, but this criterion is consistent with multiple NHLBI ARDSnet studies to date.

Patients must still meet inclusion criteria at the time of informed consent and randomization. Randomization is defined as the time that the IDS is contacted and informed about stratification of non-trauma and trauma patients. Patients that no longer meet eligibility criteria at the time of randomization are eligible to be re-screened if they meet inclusion criteria eligibility again.

Exclusion Criteria:

- 1) No consent/inability to obtain consent
- 2) Presence of pulmonary embolism
- 3) Known diffuse alveolar hemorrhage from vasculitis
- 4) Known pre-existing severe obstructive or restrictive lung disease (FEV 1 < 40% predicted, TLC < 50 % predicted) or need for long-term supplemental oxygen therapy
- 5) Known significant left ventricular systolic dysfunction with LVEF < 40% on echocardiogram.
- 6) Mean arterial pressure < 65 mmHg
- 7) Need for norepinephrine or dopamine dose > 12 mcg to maintain MAP > 65 mmHg
- 8) Severe chronic liver disease (Child-Pugh Score 11-15)

Measure	1 point	2 points	3 points	Units
Bilirubin (total)	<34 (<2)	34-50 (2-3)	>50 (>3)	μmol/l (mg/dl)
Serum Albumin	>35	28-35	<28	g/l
INR	<1.7	1.71-2.20	> 2.20	no unit
Ascites	None	Suppressed with medication	Refractory	no unit
Hepatic Encephalopathy	None	Grade I-II (or suppressed with medication)	Grade III-IV (or refractory)	no unit

- 9) Moribund patient not expected to survive 24 hours
- 10) QTc interval > 550 ms on screening bedside strip or electrocardiogram
- 11) Pregnancy or breast feeding (Women of childbearing potential, defined as < 60 years of age, will require pregnancy testing.)
- 12) Burns > 40% total body surface
- 13) Acute Neurological Disease (that may impair the ability to ventilate without assistance

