assessment of the endpoint of Ventilator Free Days (VFDs). Criterion 6 and 7 excludes patients that may have worsening of systemic hypotension due to additional effects of treprostinil. Patients with diffuse alveolar hemorrhage (criterion 3) are excluded because the mechanism of lung injury is different from ARDS/ALI due to infection. Patients with left ventricular systolic dysfunction (criterion 5) are excluded because distinguishing ARDS/ALI from pulmonary edema may be difficult and treprostinil may worsen left heart failure. For exclusion criterion 14: The recently updated clinical protocol for high flow nasal cannula use encourages flow rates beginning at 20 LPM up to 50 LPM. Invasive or non-invasive ventilation are the next options for oxygen requirements beyond 50 LPM. For exclusion criterion 15: Randomized patients are withdrawn from treatment if they require positive pressure ventilation in the form of Bi-level Positive Airway Pressure (BiPAP) or Continuous Positive Airway Pressure (CPAP), or intubation and invasive mechanical ventilation. They will receive supplemental oxygen as needed by the study protocol until that point. Unless they have comfort care only orders written, patients with pneumonia or early ARDS who are DNR receive all forms of supplemental oxygen. Therefore there is nothing in the protocol that precludes a patient who is DNR from participating. If the study drug shows a beneficial effect, the benefit would be relevant to patients who are DNR. Patients with a tracheostomy (criterion 16) would be unable to use the inhalation system. Patients that are currently receiving prostacyclin therapy (criterion 17) should be excluded to avoid the possibility of receiving excess prostacyclin therapy. Patients with a language barrier may have difficulty with instructions on how to use the inhalation device and with completing the follow up phone call. For exclusion criterion 19: Some patients with altered mental status may not be alert enough to complete the breathing pattern maneuver.

Enrollment, Randomization, and Study Initiation Time Window:

All inclusion criteria must be present concurrently. Patients must be enrolled within 24 hours of all inclusion criteria being met and identified. Information for determining when these time window criteria were met must be clearly documented.

Screening:

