Cough or pharyngitis may occur with the administration of inhaled treprostinil. It is usually mild. The investigator may choose to utilize conservative measures such as topical throat lozenges/spray or non-narcotic based antitussive medications to improve compliance with drug administration.

All enrolled patients will receive standard medical care for their acute presenting illness regardless of randomization group, including but not limited to: antibiotics, IV fluids, supplemental oxygen, and any other needed diagnostic testing or imaging.

*Premature Withdrawal from Treatment:

The following adverse effects should prompt cessation of study drug:

- 1. A drop in oxygen saturation by >/= 10 percentage points, to an absolute value of < 90%, within 15 minutes of drug administration, regardless of apparent relationship to coughing.
- 2. Severe, intractable cough resulting in worsening hypoxemia and prolonged increase in O₂ requirement (Defined as an increase of more than 2LPM O₂ that closely correlates temporarily with the cough.)
- 3. Systemic hypotension requiring increase in vasopressor dose or initiation of vasopressors due solely to the administration of study drug (i.e. not due to underlying illness such as septic shock, as determined per the discretion of the investigator) despite titrating down to previously tolerated level.
- 4. Intubation and mechanical ventilator support
- 5. Need for Bi-level Positive Airway Pressure (BiPAP) or Continuous Positive Airway Pressure (CPAP) via face mask for worsening hypoxemia.

These patients will be followed out to study completion as defined by death, 28 days from randomization, or hospital discharge whichever comes first. Discharged subjects will receive a 28 day post randomization phone assessment of disease outcomes and adverse events.

Completion of Study Drug Administration:

Patients will be considered to have completed the study drug administration portion of the study and the study drug will be stopped when one of the following conditions is met, whichever comes first:

- 1. Up to 12 days after randomization (maximum treatment period)
- 2. Discharge from study hospital. Subjects will receive a 28 day post randomization phone assessment of disease outcomes and adverse events.

3. Death

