- 11) If former smoker, when did the subject quit smoking?

Baseline Assessments

The following information will be recorded during the 24 hour interval preceding randomization. If more than one value is available for this 24 hour period, the value closest to the time of randomization will be recorded. If no values are available from the 24 hours prior to randomization, then values will be measured post randomization but prior to initiation of study drug.

- 1. APACHE II Score
- 2. LIPS Score
- 3. Vital Signs: Heart rate, systolic and diastolic blood pressure, MAP, body temperature, CVP.

Version: 02-09-2018

- 4. Arterial PaO₂, PaCO₂, pH and SpO₂
- 5. Serum AST and ALT will be documented if the data is available as standard of care
- 6. Frontal Chest Radiograph radiographic lung injury score (# of quadrants)
- 7. Vasopressors or inotropes (epinephrine, norepinephrine, phenylephrine, vasopressin, dopamine > 5 [g/kg/min, dobutamine, phosphodiesterase inhibitors)
- 8. Suspected or known site of infection (Appendix 1)
- 9. Blood for banking for future analyses
- 10. Blood for biomarkers. Plasma obtained from two, 6 ml EDTA anti-coagulated blood samples will be divided immediately after centrifugation into 12 equal 1 ml aliquots in specified tubes and frozen at -80°C. Samples will be temporarily stored in the Pulmonary Division Lab space freezers in Burnett Womack Building, or in the Emergency Room freezer. Specimens will be stored in the Koury Oral Health Sciences Building immediately adjacent to the hospital

Biomarkers: To be measured by the UNC Cytokine & Biomarker Analysis Facility, North Carolina Oral Health Institute.

```
IL-4
```

IL-6

IL-8

IL-10

IL-12

RAGE (receptor for advanced glycation end-products)

PCP (procollagen Peptide III)

Ang2 (angiopoietin 2)

MPO (myeloperoxidase)

BNP (brain natriuretic peptide)

VFW (von-Willebrand factor)

PAI-1 (plasminogen activator inhibitor 1)

SP-D (surfactant Protein D)

sICAM (soluble intracellular adhesion molecule)

Protein C

Tissue Factor

KGF (keratinocyte growth factor)

EGF (epithelial growth factor)

Soluble P-selectin

TNF α

MMP9

Procalcitonin

(Others identified from the literature as the study progresses)

Version: 02-09-2018

Reference Measurements

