The following parameters will be measured and recorded using values closest in time to Dose 1 study drug administration on days 0-11 (depending on the specific variable), or until stopping of study drug, whichever comes first. All vascular pressures will be zero-referenced to the mid-axillary line with the patient supine.

- 1) Fluid intake and output (Twenty-four hour net fluid balance)
- 2) Vital signs: Heart rate, systolic and diastolic blood pressure, body temperature, CVP
- 3) Modified Brussels Score data days 0-14:
 - a) Vasopressor use (Y/N), worst systolic BP, creatinine, bilirubin, and platelet count for the day.
- 4) Presence of myopathy
- 5) Frontal Chest Radiograph Lung Injury Score (Days 0, 3, 7 and 28)
- 6) Concomitant medications, including nebulized and inhaled medications.
- 7) Blood banked for future analyses
- 8) Biomarker samples. Plasma obtained from two, 6 ml EDTA anti-coagulated blood samples will be divided immediately after centrifugation into 12 equal 1 ml aliquots in specified tubes and frozen at –80°C. Samples will be temporarily stored in the Pulmonary Division Lab space freezers in Burnett Womack Building or in the Emergency Room freezer. Specimens will be stored in the Koury Oral Health Sciences Building. Reference biomarker list above (Days 0, 3, and 7).

Statistical Considerations/Data Analysis:

Safety

Safety will be assessed via percentage of patients and number of events recorded for the following outcomes:

- Adverse events, serious adverse events, unanticipated problems, study discontinuation overall and due to adverse event, and deaths.
- Cases of dose intolerance, including cases of worsening oxygenation, intractable cough, and systemic hypotension following dosing
- Cases of intubation or noninvasive ventilation for worsening hypoxemia

Percentages of all outcomes above will be provided to the DSMB for regular unblinded review of safety, to be assessed every 6 months or after 15 participants have completed the 28 day trial or been discharged from the hospital (whichever occurs first).

Efficacy

Version: 02-09-2018

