Federal regulations at 45 CFR 46.111(a) (1) requires that risks to subjects are minimized by using procedures which are consistent with sound research design. There are several elements of study design in the present protocol that meets this human subject protection requirement.

First, several of the exclusion criteria prohibit participation of patients who might be at increased risk from the effects of treprostinil. While many of these are considered relative contraindications in clinical care, for this trial they will be absolute contraindications.

Second, there are provisions in the protocol for reduction of the study drug for untoward or adverse effects. Similarly, there are provisions for temporary maintenance of higher doses of treprostinil during scheduled down titration if oxygenation is compromised.

Third, data at each 6 month interval or from the first 15 patients (whichever occurs first) will be evaluated by both the investigators and the DSMB to assure that there are no unrecognized adverse effects. A decision will then be made as to the safety and appropriateness of the protocol dosing regimen.

Potential Benefits

As per the background data presented, there are theoretical reasons to believe that prostacyclins (treprostinil in particular) may improve oxygenation and affect biomarkers

Version: 02-09-2018

involved or implicated in the pathogenesis of ARDS. While there may not be demonstrable benefit to individual patients in this exploratory trial due to small sample size, we may improve our understanding of the role of prostacyclin in the treatment of ARDS and mitigate safety concerns that would then allow performance of a larger, statistically rigorous trial.

Human Subjects

Each study participant or a legally authorized representative must sign and date an informed consent form. Institutional review board approval will be required before any subject is entered into the study.

Selection of Subjects

Equitable Selection of Subjects

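### Exclusion 7 limits only norepinephrine and dopamine, so patients whose MAP is held by another vasopressor, or by both drugs below the limit, are not excluded on blood-pressure or pressor grounds

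*Combined protocol and SAP*

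**What the plan says.** Two items under Exclusion Criteria concern blood pressure. Item 6 excludes "Mean arterial pressure < 65 mmHg". Item 7 excludes "Need for norepinephrine or dopamine dose > 12 mcg to maintain MAP > 65 mmHg". The Rationale for Exclusions gives their shared purpose: "Criterion 6 and 7 excludes patients that may have worsening of systemic hypotension due to additional effects of treprostinil".

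Other sections treat vasopressors more broadly. Baseline Assessments, item 7, records "Vasopressors or inotropes (epinephrine, norepinephrine, phenylephrine, vasopressin, dopamine > 5 [g/kg/min, dobutamine, phosphodiesterase inhibitors". Premature Withdrawal from Treatment, item 3, stops study drug when hypotension caused by it leads to starting or increasing a vasopressor "despite titrating down to previously tolerated level". That rule names no particular agents.

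The study proposal describes patients who present with "conditions that are conducive to ARDS (e.g. pneumonia, sepsis, aspiration, trauma"), so sepsis is among the target conditions.

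**The concern.** The risk that items 6 and 7 address is that treprostinil lowers a blood pressure that is already fragile. A MAP that stays at 65 or above only with drug support is fragile whichever pressor provides the support. Item 7 asks about two drugs, one at a time. Followed to the letter, it can admit patients of the kind it was written to keep out, and screening staff would have no written ground for refusing them.

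The dosing makes the entry rule matter more. Under Dose Rationale, the labelled start is 18 mcg, with increases every one to two weeks towards 54 mcg. This trial starts at 36 mcg and plans to reach 72 mcg within 20 hours. The protocol also acknowledges that safety in other lung diseases is not established. What is at stake is patient safety and consistent screening. Sample size, endpoint and analysis are not affected.

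**Working it through.** There is no stated figure to reproduce. The check is of wording.

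**Step 1: which criteria apply.** Of the 19 exclusions, two (items 6 and 7) concern blood pressure or pressor support. Item 9 (moribund), item 14 (imminent intubation or non-invasive ventilation) and item 19 (unable to do the breathing maneuver) may remove some very sick patients, but none of them asks about pressors.

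**Step 2: which agents are limited.** Baseline Assessments, item 7, names five vasopressors: epinephrine, norepinephrine, phenylephrine, vasopressin and dopamine. Exclusion 7 limits two of them, which leaves 5 − 2 = 3 with no limit. The other entries in the baseline item (dobutamine, phosphodiesterase inhibitors) are left aside here.

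**Step 3: apply both items to patients with MAP at 65 or above.**

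| MAP held by | Item 6 | Item 7 | Outcome |
|---|---|---|---|
| Norepinephrine or dopamine above 12 | passes | excluded | excluded |
| Norepinephrine or dopamine alone, at or below 12 | passes | passes | eligible, as the rule allows |
| Norepinephrine and dopamine together, each at or below 12 | passes | passes (no rule for adding doses) | eligible |
| Epinephrine, phenylephrine or vasopressin, any dose | passes | passes (not named) | eligible |
| One of those three added to norepinephrine at or below 12 | passes | passes | eligible |

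Here, eligible means not excluded on blood-pressure or pressor grounds. The last three rows are the gap.

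**Step 4: the unit.** Item 7 gives 12 mcg with no time or weight denominator, and the line reads as complete. The baseline item expresses its dopamine level per kg per minute and gives no rate for norepinephrine. The documents therefore do not fix the rate meant for either drug.

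**Step 5: what protects the patient after entry.**
- Treprostinil or Placebo Administration: on Day 0, blood pressure is taken before Doses 1, 3 and 5 and again no later than 30 minutes afterwards. In the Dosing Schedule these are the first dose and the two planned step-ups: 6 × 6 = 36 mcg, 9 × 6 = 54 mcg and 12 × 6 = 72 mcg.
- Dosing Schedule: during escalation, a sustained MAP fall of 15%, or a fall under 65, returns the patient to the last tolerated dose, whatever pressor is in use.
- Premature Withdrawal, item 3: applies to any vasopressor, but hypotension must be attributed solely to study drug.
- Later days: blood pressure comes from nursing flow-sheets, as close as possible before Dose 1. Reference Measurements, item 3, records "Vasopressor use (Y/N), worst systolic BP, creatinine, bilirubin, and platelet count for the day", which shows whether a pressor is used but not its dose.

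All of these act once dosing is under way. None changes who may enter.

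**Step 6: upper bound on exposure.** With 30 patients randomized 2:1, about 30 × 2/3 = 20 receive treprostinil. The share of them on an unlisted or combined pressor at entry cannot be derived and may be zero.

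**The case against.** The best case on the other side is that the wording gap has little practical effect. Day 0 monitoring covers the first dose and each planned step-up. The escalation rule responds to MAP whatever the pressor, and the withdrawal rule is generic. Dose Rationale reports no significant systemic effects below 120 mcg, and the maximum here is 72 mcg. The risk section calls systemic hemodynamic effects generally minimal. Patients must also be non-moribund, not close to intubation and able to perform the breathing maneuver, and the attending physician must agree before anyone is approached. All of this stands, and it keeps the point minor. It does not close the gap, because none of it is a pressor screen at entry.

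A reader might infer more than the documents support in four ways.
- *That item 7 was meant to exclude everyone who needs a pressor.* It excludes only above a threshold. Allowing low-dose norepinephrine or dopamine is a design choice.
- *That the protocol expects patients on the unlisted agents.* The baseline item is a list for recording data. It shows that the agents were thought of, not that such patients are anticipated.
- *That the statement "While many of these are considered relative contraindications in clinical care, for this trial they will be absolute contraindications" settles the matter.* In Minimization of Risks it refers to several exclusions without naming items 6 or 7, and it says nothing about unlisted drugs.
- *That the missing unit moves the threshold by a large multiple.* That requires one rate unit for both drugs, which the text does not state. A separate unit for each drug is the more likely intent, so such a multiple would measure an unlikely reading. The unit is a missing detail and would not carry the point alone.

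**Conclusion.** The point holds as a minor safety correction. Exclusion 7 is narrower than the purpose stated for it. Any dose of three vasopressors named elsewhere in the protocol, and combined norepinephrine and dopamine each within the limit, pass both blood-pressure criteria.

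The conclusion rests on a literal reading of the 19 exclusions and needs no numerical assumption. Its practical size is unknown: nobody may be affected, and the expected hemodynamic effect at the planned doses is small. A reader might infer that such patients would be unprotected or that the efficacy comparison is compromised. Neither follows. The post-entry safeguards apply whichever pressor is used, and the documents give no reason to think that the comparison between arms, the power or the analysis changes.

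**What to change.** Reword exclusion 7 along these lines:

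> Need for norepinephrine or dopamine above 12 [rate unit stated for each drug], or for any other vasopressor (epinephrine, phenylephrine, vasopressin), or for more than one vasopressor at the same time, to maintain MAP > 65 mmHg.

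The investigators should confirm the unit for each drug. The change is one line of the protocol and the matching line of the screening form. It keeps the existing allowance for low-dose norepinephrine or dopamine alone and needs no conversion between agents.

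There are two costs. A few patients on currently unlisted or combined pressors may become ineligible; the wording is stricter for the three added drugs, since any dose excludes. If the trial is already enrolling, as the reference to past use of the stopping rule under Study Stopping Rules suggests, patients before and after the amendment enter under different rules, and the report should say so.
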